The exposure of interest is ABRYSVO vaccination, which will be obtained from pharmacy dispensing records, general practice records, immunization registers, vaccination records, medical records, or other secondary data sources. Outcomes will be identified in participating databases with algorithms based on codes for diagnoses, procedures, and treatments. Standard algorithms for each outcome definition will be applied to participant data sources, based on the results of the ACCESS project, and will be tailored to the data source. Potential covariates may include the following information, as available in each data source: demographics; personal lifestyle characteristics; and clinical characteristics including comorbidities, comedication use, healthcare utilisation descriptors, other vaccinations, and surrogates of frailty. Covariates will be identified on the index date (or during the 12-month baseline period prior to the index date). These variables will be used to further characterize the patient populations of interest and/or to control for confounding.

Data sources

The study will utilise data from the following selected data sources: Clinical Practice Research Datalink (CPRD) Aurum (UK), Valencia Health System Integrated Database (VID) (ES), Sistema d'Informació per el Desenvolupament de la Investigació en Atenció Primària (SIDIAP) [Information System for the Improvement of Research in Primary Care] (ES), EpiChron Research Group on Chronic Diseases at the Aragon Health Sciences Institute (EpiChron) (ES), and Système National des Données de Santé (SNDS)[French nationwide healthcare database] (FR).

Study size

All individuals who meet the eligibility criteria during the study period in the select data sources will be included. The sample size will depend on the number of individuals administered ABRYSVO identified within the data sources during the study period, which will increase over time. The relative increases in rates to be detected will vary across outcomes of interest. For example, analyses using a comparative cohort design will have sufficient power (80%) to detect a 2-fold and 3-fold increased rate of arrhythmia associated with ABRYSVO, with a sample size of 1,178 and 393 individuals per cohort, respectively, assuming a baseline rate of 2,000 arrhythmia events per 100,000 person-years and equal numbers of individuals in the vaccinated and unvaccinated cohorts.

Data analysis

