9.5. Study Size

The study will be conducted in a source population of the participating population-based electronic healthcare data sources from the VAC4EU network.

Table 2 shows the sample size calculations for select outcomes (i.e, anaphylaxis, GBS, and arrhythmia) using the comparative cohort design, assuming a two-sided alpha level of 0.05, an equal number of individuals for the vaccinated and unvaccinated cohorts, and a power of 80% across a range of IRRs. Given a lack of published background incidence rates for outcomes among the specific populations of interest (i.e, adults aged 60 and older who are immunocompromised or renally impaired or hepatically impaired), published incidence rates from general populations aged 60 years and older in VAC4EU databases⁴² were used to estimate rates in the unvaccinated cohort. As an example, to detect an IRR of 2 for arrhythmia with a power of 80% and two-sided alpha level of 0.05, a sample size of 1,178 vaccinated individuals and 1,178 unvaccinated individuals is needed. This assumes a background rate of 2,000 arrythmia events per 100,000 person-years among the unvaccinated individuals.

Outcome	Background rate	Background rate	Incidence rate	Samp	le size
	per 100,000 person-years ^a	per person during risk interval ^b	ratio	Vaccinated cohort	Unvaccinated cohort
Anaphylaxis	10	0.0000005	2	47,093,279	47,093,279
			3	15,697,760	15,697,760
			5	5,886,660	5,886,660
			10	2,131,795	2,131,795
	15	0.0000008	2	29,433,300	29,433,300
			3	9,811,100	9,811,100
			5	3,679,163	3,679,163
			10	1,332,372	1,332,372
Guillain-	6	0.0000069	2	3,412,557	3,412,557
Barré syndrome			3	1,137,519	1,137,519
Synarollic			5	426,570	426,570
			10	154,478	154,478
	10	0.0000115	2	2,047,534	2,047,534
			3	682,512	682,512
			5	255,942	255,942
			10	92,687	92,687
Arrhythmia	2,000	0.0200000	2	1,178	1,178
			3	393	393

Table 2Number of Individuals Needed to Detect Different Rate Ratios for Selected
Outcomes with a Range of Background Rates

PFIZER CONFIDENTIAL CT24-WI-GL02-RF02 5.0 Non-Interventional Study Protocol Template For Secondary Data Collection Study 01-Aug-2023 Page 41 of 72

Table 2Number of Individuals Needed to Detect Different Rate Ratios for Selected
Outcomes with a Range of Background Rates

Outcome	Background rate	Background rate	Incidence rate	Samp	Sample size		
	per 100,000 person-years ^a	per person during risk interval ^b	ratio	Vaccinated cohort	Unvaccinated cohort		
			5	148	148		
			10	54	54		
	5,000	0.0500000	2	471	471		

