			3	157	157		
			5	59	59		
			10	22	22		

Notes:

a. Due to a lack of published background incidence rates of outcomes of interest among the study-specific population (i.e., adults aged 60 and older who are immunocompromised or renally impaired or hepatically impaired), background rates of outcomes among adults aged 60 and older from general European populations ,published in Supplement 1, Table 1 of Willame et al (2023)⁵³ using VAC4EU databases were used as the basis of sample size and power calculations. A range of background rates were used to address potential differences in underlying rates between the general and study-specific populations (i.e., higher and lower background incidence rates of outcomes than were published in Willame et al.). Sample size and power calculations may be updated during the study as new and relevant background rate data emerges. Key study design features will be reviewed in the light of any updated sample size and power calculations.

b. Assuming a two-sided alpha = 0.05, power of 80%, and a ratio of 1:1 of vaccinated to unvaccinated. Examples of background IR accounting for the risk window:

Anaphylaxis (10/100,000 person-years)/365 * risk window (risk window 2 days) = 0.0000005

GBS (6/100,000 person-years)/365 * risk window (risk window 42 days) = 0.0000069

Arrhythmia (2,000/100,000 person-years)/365 * risk window (risk window 365 days) = 0.02

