Individuals will be followed from the index date until death, end of administrative follow up (and/or risk interval), end of the study period, or the date of ABRYSVO/RSV vaccination (for unvaccinated individuals who later receive any RSV vaccine only), whichever occurs first. The degree of loss to follow-up will be examined. If the censoring rates differ by exposure group (i.e, indicating informative censoring) and high censoring rates (e.g., >20%) are observed, IPCW will be derived to account for informative censoring, where the weight will be calculated for each individual as the inverse of the probability of remaining uncensored during the risk interval. The stabilized IPCW will be calculated as follows, where A= vaccination, V = covariates to adjust, and C=0 represents that the patient has remained uncensored: (Pr[C=0 | A=1])/(Pr[C=0 | A=1,V=v]) for the vaccinated cohort; (Pr[C=0 | A=0])/(Pr[C=0 | A=0,V=v]) for the unvaccinated cohort.

The final weights will be calculated as the product of the ATT weight and IPCW (ATT x IPCW) if informative censoring is observed, and the ATT weight will be used as the final weight if informative censoring is not observed. The distribution of final weights (e.g., mean, SD, minimum, and maximum values) will be examined and extreme weights will be truncated or capped at the 1st and 99th percentile. After weighting, the distribution of baseline characteristics will be evaluated between the vaccinated cohort and the unvaccinated cohort, and variables that remain inadequately balanced (standardized difference >10%) between the two cohorts will be included as regression model covariates in a doubly robust approach.

Weighted Poisson regression models will be conducted to calculate IRRs of outcomes among vaccinated cohort vs. unvaccinated cohort. Incidence rate ratios will be summarized, and robust variance estimators will be used to calculate the corresponding 95% CIs.

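### Table 2 sizes the anaphylaxis rows from an over-rounded rate, states 80% power for an unweighted test that is not the planned analysis, and rests its IRR 10 rows on about one comparator event

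*Protocol*

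**What the plan says.** Section 9.5 sizes anaphylaxis, GBS and arrhythmia at two background rates each, for "a power of 80% across a range of IRRs" (2, 3, 5 and 10) and with "an equal number of individuals for the vaccinated and unvaccinated cohorts". Note b repeats the settings: "Assuming a two-sided alpha = 0.05, power of 80%, and a ratio of 1:1 of vaccinated to unvaccinated". It also shows how a yearly rate becomes a per-person rate over the risk window, for instance "Anaphylaxis (10/100,000 person-years)/365 * risk window (risk window 2 days) = 0.0000005". The same conversion is shown for GBS at 6/100,000 over 42 days, printed as 0.0000069, and for arrhythmia at 2,000/100,000 over a full year, printed as 0.02.

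The abstract takes up the arrhythmia rows: "analyses using a comparative cohort design will have sufficient power (80%) to detect a 2-fold and 3-fold increased rate of arrhythmia associated with ABRYSVO", at 1,178 and 393 per cohort.

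The analysis is fixed in section 9.7.3.1. Unvaccinated people are weighted by PS/(1-PS), possibly multiplied by a censoring weight. Then: "Weighted Poisson regression models will be conducted to calculate IRRs of outcomes among vaccinated cohort vs. unvaccinated cohort", with robust variance for the confidence intervals.

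**The concern.** Three things do not fit together. The printed anaphylaxis rate is not what note b's formula gives. The sizes make no allowance for the weighting that section 9.7.3.1 prescribes, although unequal comparator weights ordinarily raise the variance of the comparator rate. At the largest rate ratio the table needs so few people that hardly any comparator events are expected, and a Poisson rate ratio may then have no finite estimate.

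At stake is how the regulator reads the stated 80%, and what any later review of the study size is compared with. Note a to Table 2 says key design features will be reviewed against updated calculations.

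**Working it through.** **Inputs.** From section 9.5 and its notes: two-sided alpha 0.05, power 80%, 1:1 cohorts, IRR 2/3/5/10, and the per-person rates r. The design effect D (inflation of comparator variance by weighting) is not in the documents; 1.25, 1.5 and 2 are assumptions.

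**Reproducing the table.** All 24 rows reproduce to the unit, using the printed r, from

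n = (1.95996 + 0.84162)² × (1 + IRR) / [r × (IRR − 1)²], where (1.95996 + 0.84162)² = 7.8489.

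This is an unweighted normal test on the rate difference. For example:
- Anaphylaxis, r = 5e-7, IRR 2: 7.8489 × 3 / 5e-7 = 47,093,279.
- Arrhythmia, r = 0.02, IRR 2: 7.8489 × 3 / 0.02 = 1,178. IRR 3: 7.8489 × 4 / (0.02 × 4) = 393.

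**1. Rounding.** Note b's formula gives 10/100,000/365 × 2 = 5.479e-7 and 15/100,000/365 × 2 = 8.219e-7. The table uses 5e-7 and 8e-7.

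| Rate per 100,000 | IRR | Stated n | n from unrounded rate |
|---|---|---|---|
| 10 | 2 | 47,093,279 | 42,972,617 |
| 10 | 3 | 15,697,760 | 14,324,206 |
| 10 | 5 | 5,886,660 | 5,371,578 |
| 10 | 10 | 2,131,795 | 1,945,263 |
| 15 | 2 | 29,433,300 | 28,648,412 |
| 15 | 3 | 9,811,100 | 9,549,471 |
| 15 | 5 | 3,679,163 | 3,581,052 |
| 15 | 10 | 1,332,372 | 1,296,842 |

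The ratios are 5.479/5 = 1.096 and 8.219/8 = 1.027, so the stated sizes are 9.6% and 2.7% too large. By the same formula their power is about 83.5% and 81.0%. The effect is 0.06% for GBS and nil for arrhythmia.

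**2. Weighting.** On the table's own scale, with m0 = n × r comparator events expected, power = Φ(m0(IRR − 1)/√[m0(D + IRR)] − 1.96). At 1,178, m0 = 23.56; at 393, m0 = 7.86. The second method simulates the log-IRR Wald test with a robust-type variance and lognormal comparator weights.

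| Arrhythmia row | Method | D = 1.25 | D = 1.5 | D = 2 |
|---|---|---|---|---|
| 1,178, IRR 2 | Rate difference | 77% | 74% | 68% |
| 1,178, IRR 2 | Simulated Wald | 75% | 69% | 62% |
| 393, IRR 3 | Rate difference | 78% | 75% | 71% |
| 393, IRR 3 | Simulated Wald | 74% | 69% | 64% |

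Without weighting, the enumerated Wald test has 80.4% (IRR 2) and 81.1% (IRR 3), so the shortfall comes from the assumed D.

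**3. Comparator events.** Since n is proportional to 1/r, the expected comparator count depends only on the IRR (apart from rounding up): m0 = 7.8489 × (1 + IRR)/(IRR − 1)². Power below is by full Poisson enumeration without weighting; a zero comparator count is scored as no detection for the Wald test.

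| IRR | m0 | P(zero) = exp(−m0) | Log-IRR Wald | Score | Likelihood ratio | Exact conditional |
|---|---|---|---|---|---|---|
| 2 | 23.5 | about 0 | 80.4% | 81.0% | 81.2% | 77.7% |
| 3 | 7.8 | 0.04% | 81.1% | 82.7% | 82.9% | 76.6% |
| 5 | 2.9 | 5.3% | 75.9% | 84.1% | 85.9% | 77.9% |
| 10 | 1.07 | 34.4% | 46.8% | 86.2% | 90.8% | 78.8% |

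For the 10/100,000 anaphylaxis rows, the surplus from rounding lifts the Wald figures to 81.3% at IRR 5 and 54.2% at IRR 10.

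**The case against.** The strongest reply is that Table 2 is a planning approximation, exactly consistent with its printed inputs, and that its background rates are far less certain than any of this: arrhythmia is bracketed at 2,000 and 5,000 per 100,000. At 5,000, the 1,178 per cohort would have m0 = 58.9 and power Φ(58.9/√(58.9 × 3) − 1.96), about 99%. The abstract sentence is introduced as an example and states its rate and its equal cohorts. Note a allows the calculations to be updated. All of that is true. But the update is tied to new background rates, which would correct neither the missing weighting nor the sparse rows, and the abstract's 80% carries no caveat about weighting.

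Some stronger readings are tempting, and the documents do not support them:

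- *The rounding costs power.* It does the reverse. For the 10/100,000 anaphylaxis rows its surplus would absorb a design effect of about 1.29 at IRR 2. The arrhythmia rows quoted in the abstract have no such surplus.
- *The planned analysis certainly misses 80%.* The protocol supplies no design effect, so the loss is conditional on an assumed one. Nor should it be sized from the closed-form log-IRR formula, which gives 72/66/57% and 69/62/52% but already starts at 78% and 76% with no weighting.
- *Near-zero comparator counts undermine the whole table.* Only the IRR 10 rows are near one event. The 47% also depends on Wald inference, which is the natural reading of robust-variance intervals for a Poisson IRR, but the protocol names no test.
- *The study should draw several comparators per vaccinee instead of 1:1.* The 1:1 ratio is a calculation assumption. Sections 9.1 and 9.1.1 call for a random sample of unvaccinated people and fix no ratio, so there is no error to correct.

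**Conclusion.** The point holds in three limited parts.

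1. The anaphylaxis sizes are wrong by note b's own formula: 9.6% too large at 10/100,000 and 2.7% at 15/100,000, on the conservative side. This rests on no assumption.
2. The 80% in Table 2 and the abstract describes an unweighted test that is not the planned one. The mismatch is certain; its size is not. For assumed comparator variance inflation of 1.25 to 2, power lies between about 77% and 62% at 1,178 per cohort, and between about 78% and 64% at 393, depending on D and the test scale.
3. The IRR 10 rows rest on 1.07 expected comparator events, with a 34% chance of no finite IRR and about 47% Wald power. IRR 5 is affected mildly (76%). Score or likelihood-ratio tests would exceed 80% in both.

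None of this questions the choice of design or model. It should be corrected because the protocol itself states the sizes and the power.

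**What to change.** - Recompute the eight anaphylaxis rows from unrounded rates, and print those rates to at least three significant figures.
- Label Table 2 and the abstract sentence as unweighted, and add power over a stated range of assumed design effects, saying which test and scale are used.
- Replace or caveat the IRR 5 and IRR 10 rows with exact or simulated power for the planned estimator, including how a zero comparator count is handled.

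The cost is a recalculated table, a short note and one abstract sentence. The anaphylaxis sizes fall slightly, and the power shown for the planned analysis may look less favourable. No change to data collection or to the sampling of comparators is needed.

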9.1.1. Primary Design - Comparative Cohort Design

A comparative cohort design will be used to estimate incidence rates and incidence rate ratios of prespecified outcomes among immunocompromised, or renally impaired, or hepatically impaired older adults with and without receipt of the ABRYSVO vaccine. Individuals in the unvaccinated cohort must have no record of an RSV vaccine on the index date or in the baseline period prior to index date or any other vaccine on the index date but can later receive ABRYSVO and enter the vaccinated cohort if all eligibility criteria are met. To address possible selection bias due to health seeking behaviours, unvaccinated individuals will be randomly selected from a population of patients who have regular use of preventive medical care, defined as at least one vaccination record in the year prior to the index date. The baseline period is defined as 12 months prior to the index date. The follow-up period will begin from day 1 (the day after ABRYSVO administration for vaccinated cohort, or the day after matched index date for the unvaccinated cohort) and continue to the earliest occurrence of an outcome, date of RSV vaccination (for unvaccinated individuals who later receive any RSV vaccine only), the end of administrative follow-up, end of the study period, or death. For those outcomes with a defined risk window, follow-up will also be truncated at the end of the risk window. To enhance comparability between the vaccinated and unvaccinated cohorts, ATT weights will be used. Weights, based on PS, will incorporate additional measures of healthcare utilization in the baseline period to further account for potential differences in healthcare seeking behaviour between the vaccinated and unvaccinated cohorts. However, as this study focuses on patients with chronically managed conditions, differences in healthcare seeking behaviour are not anticipated. IPCW will also be employed if informative censoring (i.e., differential rates of censoring during follow up) and high censoring rates are observed between the vaccinated and unvaccinated cohorts. Examples of patient follow-up scenarios are depicted in Figure 1 and Figure 2. Comparative analyses will also include variables that remain inadequately balanced between the two cohorts in a doubly robust approach. Further details are provided in Section 9.7.2 and Section 9.7.3.

Figure 1 Comparative Cohort Design

[figure not shown]

Notes:

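### The arrhythmia sample sizes are person-years labelled as individuals: with follow-up that the plan itself cuts short, 1,178 people per cohort give less than the stated 80% power

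*Protocol*

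**What the plan says.** Section 9.5 sizes the comparative cohort design "assuming a two-sided alpha level of 0.05, an equal number of individuals for the vaccinated and unvaccinated cohorts". For its worked arrhythmia example (IRR 2, 80% power, the same alpha) it concludes that "a sample size of 1,178 vaccinated individuals and 1,178 unvaccinated individuals is needed". The rate assumption follows: "This assumes a background rate of 2,000 arrythmia events per 100,000 person-years among the unvaccinated individuals".

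Note b to Table 2 shows how that rate becomes an expected count per person: "Arrhythmia (2,000/100,000 person-years)/365 * risk window (risk window 365 days) = 0.02".

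The abstract repeats the result as sufficient for 80% power to detect 2-fold and 3-fold increases, "with a sample size of 1,178 and 393 individuals per cohort, respectively". The only assumptions it names are the baseline rate and equal cohort sizes.

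The follow-up rules are elsewhere. Section 9.1.1 ends follow-up at the first outcome, death, end of administrative follow-up, end of the study period or, for one cohort only, "date of RSV vaccination (for unvaccinated individuals who later receive any RSV vaccine only"). Section 9.2.4 describes follow-up of at most 12 months, and Section 9.2.1 requires only one day of it for eligibility. Section 9.7.3.1 provides censoring weights if censoring differs by exposure group and "high censoring rates (e.g., >20%) are observed".

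**The concern.** Multiplying an annual rate by a 365-day window gives the expected count per person only if each person is observed for all 365 days. For a one-year outcome that makes one individual equal to one person-year. The figures 1,178 and 393 are therefore amounts of person-time, but the text calls them individuals.

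The plan guarantees that some people contribute less than a year, and Section 9.5 makes no allowance for it. The same head count then yields fewer events and less power than stated. At stake is the accuracy of a power statement that is made prominently in the abstract and would be the benchmark for judging whether accrual is adequate for arrhythmia.

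**Working it through.** **Inputs from the protocol (Section 9.5, Table 2 and notes):** two-sided alpha 0.05, power 80%, 1:1 allocation, background rate 2,000 per 100,000 person-years, window 365 days. Hence λ0 = 0.02 and, for IRR 2, λ1 = 0.04 expected events per person.

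**Step 1: reproduce the stated figure.** Comparing two Poisson rates on the difference scale:

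n = (z₀.₉₇₅ + z₀.₈₀)² × (λ0 + λ1) / (λ1 − λ0)², with (1.95996 + 0.84162)² = 7.8489.

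- IRR 2: 7.8489 × 0.06 / 0.0004 = 1,177.33, rounded up to 1,178.
- IRR 3: 7.8489 × 0.08 / 0.0016 = 392.44, rounded up to 393.

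The same formula returns all eight arrhythmia rows exactly (1,178, 393, 148, 54 at the 2,000 rate; 471, 157, 59, 22 at the 5,000 rate). No follow-up or dropout factor is involved. Power at n = 1,178 is 80.02%.

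**Step 2: allow for incomplete follow-up.** Let fv and fc be the mean years observed per vaccinated person and per comparator. The rates are unchanged; only the variance grows:

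- n = 7.8489 × (λ1/fv + λ0/fc) / (λ1 − λ0)²
- power = Φ( (λ1 − λ0) / √[λ1/(n·fv) + λ0/(n·fc)] − 1.96 )

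**Step 3: the loss that follows from the plan's own rules.** Follow-up stops at the first outcome. With constant rates and no other censoring, mean follow-up is (1 − e^−λ)/λ:

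- comparator: (1 − e^−0.02)/0.02 = 0.9901
- vaccinated: (1 − e^−0.04)/0.04 = 0.9803

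The variance term becomes 0.04/0.9803 + 0.02/0.9901 = 0.0610. Then n = 7.8489 × 0.0610060/0.0004 = 1,197.07, rounded up to 1,198, and power at 1,178 is 79.4%.

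**Step 4: further censoring (assumed range).** The protocol gives no mean follow-up and no expected censoring rate, so these are scenarios and not estimates.

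| Mean years, vaccinated / comparator | Power at 1,178 (IRR 2) | n per cohort for 80% |
|---|---|---|
| 1.00 / 1.00 | 80.0% | 1,178 |
| 0.95 / 0.95 | 78.0% | 1,240 |
| 0.90 / 0.90 | 75.8% | 1,309 |
| 0.90 / 0.80 | 74.1% | 1,363 |
| 0.80 / 0.80 | 70.8% | 1,472 |

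Example, 0.90/0.80: 0.04/0.90 + 0.02/0.80 = 0.06944; 7.8489 × 0.06944/0.0004 = 1,362.7, rounded up to 1,363.

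The other arrhythmia rows behave alike. At 0.90/0.80, 393 per cohort for IRR 3 has 74.5% power (n = 450 needed), and 471 per cohort for IRR 2 at the 5,000 rate has 74.0%.

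**Step 5: which cohort's loss matters more.** With 0.80 years in one cohort and a full year in the other, power at 1,178 is 76.8% if only comparators lose time and 73.7% if only the vaccinated do. With IRR 2, the vaccinated term λ1/fv carries twice the weight.

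**The case against.** The strongest reply is that this is an open simplification and not a slip. Note b shows the multiplication by 365 days, the Table 2 column is headed as a rate per person during the risk interval, and every row reproduces. That is fair: the arithmetic is internally right. It does not rescue the label, because Section 9.5 and the abstract state the result as individuals needed for 80% power without saying that complete follow-up is assumed.

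The size of the shortfall is assumed, and it may be small. Section 9.2.4 plans data collection to allow 12 months after vaccination, so truncation at the end of the study is largely designed out, and the one-day minimum is an eligibility floor that says nothing about the mean. At 5% lost person-time the deficit is about 2 points. It is also small beside the uncertainty that Table 2 already displays: moving from 2,000 to 5,000 per 100,000 changes n from 1,178 to 471. All of this stands and limits the point's weight.

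Stronger readings are tempting, but the documents do not support them:

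- **That the protocol expects more than 20% censoring.** The figure in Section 9.7.3.1 is an example trigger for using censoring weights, conditional on what is observed; it is not a forecast.
- **That censoring comparators at RSV vaccination is the main threat to power.** Step 5 shows that the same loss of time costs more in the vaccinated cohort.
- **That the study will be underpowered for arrhythmia.** The abstract says all eligible individuals are included, and 1,178 is introduced as an example. Nothing stops accrual at that number.
- **That the error will distort decisions on adding vaccination seasons.** Section 9.2.4 ties these to uptake and exposure accrual, and note a to Table 2 mentions updated calculations only as new background rates emerge. A link to the head count is speculation.

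Two defences do not hold. Censoring weights address bias and do not restore lost events. And since the figure is stated in the protocol and its abstract, correcting it cannot be left to the statistical analysis plan.

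**Conclusion.** The point holds as a correction to a stated power figure. The arrhythmia entries in Table 2, Section 9.5 and the abstract are person-years per cohort presented as individuals. With the plan's own stopping rules, the stated number of individuals gives less than 80% power.

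Only the first-event loss follows from the plan's rules and rates (79.4%, n about 1,198, constant rates assumed), and it is trivial by itself. Anything beyond that rests on assumed mean follow-up: about 78% if 5% of person-time is lost in both cohorts, and 74% to 76% in the scenarios with a mean of 0.90 years in the vaccinated and 0.80 to 0.90 in comparators. All figures use the protocol's own difference-scale formula and its 2,000 per 100,000 rate. The anaphylaxis and GBS rows, with windows of 2 and 42 days, are hardly affected.

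**What to change.** In Table 2, Section 9.5 and the abstract, do one of the following for the arrhythmia figures:

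1. Restate them as person-years per cohort (for example 1,178 and 393), saying that as head counts they assume complete 365-day follow-up for everyone.
2. Keep individuals as the unit, but give the number over an explicitly assumed range of mean follow-up per cohort, such as the range tabulated above, marked as assumptions.

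Under either option, update the statement with the follow-up observed by cohort at the interim report. That fits its descriptive scope, since it needs person-time only and no comparison of outcomes.

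The cost is a relabelled or extended block of Table 2 and one sentence each in Section 9.5 and the abstract. Design, eligibility and analysis are unchanged; under the second option the stated requirement becomes somewhat larger.
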